## 5.2 Exclusion Criteria

1. Patients having no lesions outside the field of radiation thus nullifying the ability to measure

an abscopal effect;

2. Autoimmune disease: Patients with a history of inflammatory bowel disease are excluded from this study as are patients with a history of symptomatic auto immune disease (e.g., rheumatoid arthritis, progressive systemic sclerosis [scleroderma]), systemic lupus erythematosus, autoimmune vasculitis [e.g., Wegener's granulomatosis];
3. Patients with a history of symptomatic interstitial lung disease OR a history of (non-infectious) pneumonitis that required oral or IV steroids or current pneumonitis. Patients with resolved RT pneumonitis are eligible.
4. Patients with uncontrolled HIV infection. Note: participants with a plasma HIV viral load less than 200 copies/mL are eligible.
5. Patients with active Hepatitis B and Hepatitis C infection. Patients undergoing active therapy will be excluded from the trial.
6. Any underlying medical or psychiatric condition, which in the opinion of the Investigator, will make the administration of study drug hazardous or obscure the interpretation of adverse events (AEs), such as a condition associated with frequent diarrhea;
7. Concomitant therapy with any of the following: IL-2, interferon or other non-study immunotherapy regimens; cytotoxic chemotherapy; immunosuppressive agents; other investigation therapies; or chronic use of systemic corticosteroids; Tyrosine Kinase inhibitors such as Erlotinib;
8. Women and men who are unwilling or unable to use an acceptable method to avoid pregnancy for the entire study period and for at least 5mos (women) or 7mos(men) weeks after cessation of study drug, or have a positive pregnancy test at baseline, or are pregnant or breastfeeding;
9. Prisoners or subjects who are compulsorily detained (involuntarily incarcerated) for treatment of either a psychiatric or physical (e.g., infectious) illness.
10. Patients with mixed NSCLC/SCLC histology are excluded from this trial.

## 6.0 STUDY THERAPY

Each patient will receive ipilimumab intravenously at 3 mg/kg on C1D1. Infusions will be given over 30minutes (not bolus or i.v. push).

Ipilimumab 3mg/kg will be administered on Day 1. On Day 22, ipilimumab (1mg/kg) will be given along with nivolumab (360mg). Subsequently, ipilimumab (1mg/kg) will be given every 6 weeks and nivolumab (360mg) will be given every 3 weeks.

Radiation will be delivered daily, Monday-Friday, for five consecutive days, at the Stich Radiation or DHK Radiation Oncology at Weill Comell Medicine-New York Presbyterian. A dose of 6 Gy x 5 days will be tested. All patients will be re-imaged by CT on Day 70 ( $\pm$ 7 days).

### PRODUCT INFORMATION TABLE:

Product Description and Dosage Form	Potency	Primary Packaging	Appearance	Storage (per label)	Conditions
-------------------------------------	---------	-------------------	------------	---------------------	------------

		(Volume)/ Label Type		
Nivolumab BMS-936558-01 Solution for Injection a	100 mg (10 mg/mL)	10 mL vial	Clear to opalescent colorless to pale yellow liquid. May contain particles	2 to 8°C. Protect from light and freezing
Ipilimumab Solution for Injection	200 mg (5 mg/mL)	40 mL vial	Clear, colorless to pale yellow liquid. May contain particles	2 to 8°C. Protect from light and freezing.

\*Nivolumab may be labeled as BMS-936558-01 Solution for Injection

If stored in a glass front refrigerator, vials should be stored in the carton. Recommended safety measures for preparation and handling of nivolumab and ipilimumab include laboratory coats and gloves.

For additional details on prepared drug storage and use time of nivolumab or ipilimumab under room temperature/light and refrigeration, please refer to the BMS-936558 (nivolumab) and ipilimumab Investigator Brochure section for "Recommended Storage and Use Conditions"

#### Handling and Dispensing

*The investigator should ensure that the study drug is stored in accordance with the environmental conditions (temperature, light, and humidity) as per product information and the Investigator Brochure and per local regulations. It is the responsibility of the investigator to ensure that investigational product is only dispensed to study subjects. The investigational product must be dispensed only from official study sites by authorized personnel according to local regulations. If concerns regarding the quality or appearance of the study drug arise, the study drug should not be dispensed and contact BMS immediately.*

*Please refer to the current version of the Investigator Brochure and/or shipment reference sheets for additional information on storage, handling, dispensing, and infusion information for nivolumab.*

#### Destruction

Sponsor/Investigator drug destruction is allowed provided the following minimal standards are met:

- On-site disposal practices must not expose humans to risks from the drug.
- On-site disposal practices and procedures are in agreement with applicable laws and regulations, including any special requirements for controlled or hazardous substances.
- Written procedures for on-site disposal are available and followed. The procedures must be filed with the Sponsor SOPs and a copy provided to BMS upon request.
- Records are maintained that allow for traceability of each container, including the date disposed of, quantity disposed, and identification of the person disposing the containers. The method of disposal, i.e, incinerator, licensed sanitary landfill, or licensed waste disposal vendor must be documented.
- Accountability and disposal records are complete, up-to-date, and available for BMS to review throughout the clinical trial period as per the study agreement.

If conditions for destruction cannot be met, please contact BMS.

It is the Sponsor Investigator's responsibility to arrange for disposal of all empty containers, provided that procedures for proper disposal have been established according to applicable federal, state, local, and institutional guidelines and procedures, and provided that appropriate records of disposal are kept.

#### Dose calculations and administration

Describe timing of first dose from registration/randomization. For preparation and administration details to be included in your protocol [per institutional policies], please refer to the current Investigator Brochure, (Section 3.2) and/or pharmacy reference Appendix.

Day 1 ipilimumab will be given at a dosing of 3mg/kg. On day 22, nivolumab (360mg) and ipilimumab (1mg/kg) will be given together. Subsequently, ipilimumab (1mg/kg) will be given every 6 weeks and nivolumab (360mg) every 3 weeks. Both nivolumab and ipilimumab can be administered over 30 minutes.

When study drugs (ipilimumab or nivolumab) are to be administered on the same day, separate infusion bags and filters must be used for each infusion. It is recommended that nivolumab be administered first. The second infusion will always be ipilimumab, and will start approximately 30 minutes after completion of the nivolumab infusion.

Ipilimumab and nivolumab may be diluted in 0.9% Sodium Chloride Solution or 5% Dextrose solution.

The dosing calculations should be based on the body weight. If the subject's weight on the day of dosing differs by > 10% from the weight used to calculate the dose, the dose must be recalculated. All doses should be rounded up or to the nearest milligram per institutional standard.

Following the first doses of the combination of nivolumab and ipilimumab on day 22, nivolumab will be given every three weeks at a dose of 360 mg. Patients may be dosed no less than 12 days from the previous dose of drug; and dosed up to 3 days after the scheduled date if necessary.

#### **Dose Modifications**

There will be no dose modifications permitted. Dose reductions or dose escalations are not permitted.

#### **Management Algorithms for Immuno-Oncology Agents**

Immuno-oncology (I-O) agents are associated with adverse events that can differ in severity and duration than adverse events caused by other therapeutic classes. Nivolumab and ipilimumab are considered immuno-oncology agents in this protocol. Management algorithms have been developed to assist investigators in assessing and managing the following groups of adverse events: Gastrointestinal, Renal, Pulmonary, Hepatic, Endocrinopathies, Skin, and Neurological.

Early recognition and intervention are recommended according to the management algorithms; and in addition include ophthalmologic evaluations for any visual symptoms in order to evaluate for nivolumab or ipilimumab related uveitis.

The recommendations are to follow the algorithms in the nivolumab investigator brochure for immune related events; while the ipilimumab investigator brochure contains similar algorithms, the algorithms in the nivolumab brochure have been aligned to accommodate combinations as

well as nivolumab monotherapy.

Therefore, the algorithms recommended for utilization are attached for reference.

For subjects expected who require more than 4 weeks of corticosteroids or other immunosuppressants to manage an adverse event, consider the following recommendations

Antimicrobial/antifungal prophylaxis per institutional guidelines to prevent opportunistic infections such as *Pneumocystis jiroveci* and fungal infections.

Early consultation with an infectious disease specialist should be considered. Depending on the presentation, consultation with a pulmonologist for bronchoscopy or a gastroenterologist for endoscopy may also be appropriate.

In patients who develop recurrent adverse events in the setting of ongoing or prior immunosuppressant use, an opportunistic infection should be considered in the differential diagnosis.

Additional details on the safety of nivolumab and ipilimumab, including results from clinical studies, are available in the IB.

### **Dose Delay Criteria**

Because of the potential for clinically meaningful nivolumab-related AEs requiring early recognition and prompt intervention, management algorithms have been developed for suspected AEs of selected categories.

Dose delay criteria apply for all drug-related adverse events (regardless of whether or not the event is attributed to nivolumab, ipilimumab or both). All study drugs must be delayed until treatment can resume.

Nivolumab and ipilimumab administration should be delayed for the following:

- Any Grade  $\geq 2$  non-skin, drug-related adverse event, with the following exceptions:
- Grade 2 drug-related fatigue or laboratory abnormalities do not require a treatment delay
- Any Grade 3 skin, drug-related adverse event
- Any Grade 3 drug-related laboratory abnormality, with the following exceptions for asymptomatic amylase or lipase, AST, ALT, or total bilirubin:
  - Grade 3 amylase or lipase abnormalities that are not associated with symptoms or clinical manifestations of pancreatitis do not require a dose delay. It is recommended to consult with the principle investigator for Grade 3 amylase or lipase abnormalities.
  - If a subject has a baseline AST, ALT, or total bilirubin that is within normal limits, delay dosing for drug-related Grade  $\geq 2$  toxicity
  - If a subject has baseline AST, ALT, or total bilirubin within the Grade 1 toxicity range, delay dosing for drug-related Grade  $\geq 3$  toxicity
  - Any adverse event, laboratory abnormality, or intercurrent illness which, in the judgment of the investigator, warrants delaying the dose of study medication.

### **Criteria to Resume Treatment**

Subjects may resume treatment with study drug when the drug-related AE(s) resolve to Grade ≤1 or baseline value, with the following exceptions:

- Subjects may resume treatment in the presence of Grade 2 fatigue
- Subjects who have not experienced a Grade 3 drug-related skin AE may resume treatment in the presence of Grade 2 skin toxicity
- Subjects with baseline Grade 1 AST/ALT or total bilirubin who require dose delays for reasons other than a 2-grade shift in AST/ALT or total bilirubin may resume treatment in the presence of Grade 2 AST/ALT OR total bilirubin
- Subjects with combined Grade 2 AST/ALT AND total bilirubin values meeting discontinuation parameters should have treatment permanently discontinued
- Drug-related pulmonary toxicity, diarrhea, or colitis, must have resolved to baseline before treatment is resumed
- Drug-related endocrinopathies adequately controlled with only physiologic hormone replacement may resume treatment

If the criteria to resume treatment are met, the subject should restart treatment at the next scheduled timepoint per protocol. However, if the treatment is delayed past the next scheduled timepoint per protocol, the next scheduled timepoint will be delayed until dosing resumes. If the design of the study defines that doses may not be omitted [skipped], strongly recommend adding "Doses may not be skipped"

If treatment is delayed > 6 weeks, the subject must be permanently discontinued from study therapy, except as specified in discontinuation section.

### **Discontinuation Criteria**

Treatment should be permanently discontinued for the following:

Any Grade 2 drug-related uveitis or eye pain or blurred vision that does not respond to topical therapy and does not improve to Grade 1 severity within the re-treatment period OR requires systemic treatment

Any Grade 3 non-skin, drug-related adverse event lasting > 7 days, with the following exceptions for drug-related laboratory abnormalities, uveitis, pneumonitis, bronchospasm, diarrhea, colitis, neurologic adverse event, hypersensitivity reactions, and infusion reactions

Grade 3 drug-related uveitis, pneumonitis, bronchospasm, diarrhea, colitis, neurologic adverse event, hypersensitivity reaction, or infusion reaction of any duration requires discontinuation

Grade 3 drug-related laboratory abnormalities do not require treatment discontinuation except those noted below

Grade 3 drug-related thrombocytopenia > 7 days or associated with bleeding requires discontinuation

Any drug-related liver function test (LFT) abnormality that meets the following criteria require discontinuation:

- AST or ALT > 8 x ULN
- Total bilirubin > 5 x ULN
- Concurrent AST or ALT > 3 x ULN and total bilirubin > 2 x ULN

Any Grade 4 drug-related adverse event or laboratory abnormality, except for the following events which do not require discontinuation:

Isolated Grade 4 amylase or lipase abnormalities that are not associated with symptoms or clinical manifestations of pancreatitis and decrease to < Grade 4 within 1 week of onset.

- Isolated Grade 4 electrolyte imbalances/abnormalities that are not associated with clinical sequelae and are corrected with supplementation/appropriate management within 72 hours of their onset
- Any dosing interruption lasting > 6 weeks with the following exceptions:
- Dosing interruptions to allow for prolonged steroid tapers to manage drug-related adverse events are allowed. Prior to re-initiating treatment in a subject with a dosing interruption lasting > 6 weeks, the Investigator must be consulted. Tumor assessments should continue as per protocol even if dosing is interrupted
- Dosing interruptions > 6 weeks that occur for non-drug-related reasons may be allowed if approved by the Investigator. Prior to re-initiating treatment in a subject with a dosing interruption lasting > 6 weeks, the Investigator must be consulted. Tumor assessments should continue as per protocol even if dosing is interrupted
- Any adverse event, laboratory abnormality, or intercurrent illness which, in the judgment of the Investigator, presents a substantial clinical risk to the subject with continued nivolumab or ipilimumab dosing

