## APPENDIX 4 Hepatotoxicity Management Algorithm

## Hepatic Adverse Event Management Algorithm

Rule out non-inflammatory causes. If non-inflammatory cause, treat accordingly and continue I-O therapy. Consider imaging for obstruction.

Patients on IV steroids may be switched to an equivalent dose of oral corticosteroids (e.g. prednisone) at start of tapering or earlier, once sustained clinical improvement is observed. Lower bioavailability of oral corticosteroids should be taken into account when switching to the equivalent dose of oral corticosteroids.

\*I-O therapy may be delayed rather than discontinued if AST/ALT  $\leq$  8 x ULN or T.bili  $\leq$  5 x ULN.

[figure not shown]
\*\*The recommended starting dose for grade 4 hepatitis is 2 mg/kg/day methylprednisolone IV.

Updated 05-Jul-2016

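### The Appendix 4 liver footnote allows dosing to be delayed for combined AST/ALT and bilirubin elevations that Section 6.0 makes a permanent stop

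*Combined protocol and SAP*

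**What the plan says.** **Section 6.0, Discontinuation Criteria.** Drug-related liver abnormalities require permanent discontinuation in three situations: AST or ALT above 8 x ULN, total bilirubin above 5 x ULN, or "Concurrent AST or ALT > 3 x ULN and total bilirubin > 2 x ULN".

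**Section 6.0, Criteria to Resume Treatment.** The combined case is repeated: "Subjects with combined Grade 2 AST/ALT AND total bilirubin values meeting discontinuation parameters should have treatment permanently discontinued".

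**Appendix 4, Hepatotoxicity Management Algorithm.** A footnote reads "I-O therapy may be delayed rather than discontinued if AST/ALT" is at or below "8 x ULN or T.bili" is at or below 5 x ULN. The visible text says nothing about both values being raised at once.

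**Section 6.0, Management Algorithms for Immuno-Oncology Agents.** Investigators are recommended to follow the algorithms for immune-related events. The same subsection describes the algorithms as assistance and attaches them for reference. It does not say which text governs when an algorithm and the Discontinuation Criteria differ.

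**The concern.** The footnote carries over the first two liver limits of Section 6.0 (8 x and 5 x ULN) but not the third, the combined one. Sites are told to use the algorithm. A physician who manages a liver event from Appendix 4 could therefore hold treatment and later restart ipilimumab and nivolumab in a patient who must stop permanently under Section 6.0. Safety of the regimen is a primary objective in Section 3.0 and the trial runs at two centers, so the stop rule should read the same wherever it appears.

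**Working it through.** No sample size or error rate is involved. The check is whether the two rules can both apply to one patient.

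**Inputs.** Let *a* be AST or ALT and *b* total bilirubin, both in multiples of ULN, for a drug-related elevation.

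- Stop rule (Section 6.0): *a* > 8, or *b* > 5, or (*a* > 3 and *b* > 2).
- Footnote as written (Appendix 4): delay if *a* ≤ 8 or *b* ≤ 5.
- Footnote with 'or' read as 'and': delay if *a* ≤ 8 and *b* ≤ 5.
- Proposed footnote: delay if *a* ≤ 8 and *b* ≤ 5 and not (*a* > 3 and *b* > 2).

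**Step 1, the 'and' reading.** If *a* ≤ 8 and *b* ≤ 5, the first two stop conditions are false, so a stop can come only from the combined condition. The overlap of stop and delay is exactly 3 < *a* ≤ 8 with 2 < *b* ≤ 5.

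**Step 2, the literal 'or' reading.** Delay is refused only when *a* > 8 and *b* > 5 together. Every other liver stop in Section 6.0 then overlaps with permission to delay, including patients over just one of the two single-parameter limits.

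**Step 3, the proposed wording.** Negating the stop rule gives *a* ≤ 8 and *b* ≤ 5 and not (*a* > 3 and *b* > 2), which is the proposed footnote term for term. No patient meets both rules and none falls between them.

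**Worked values.**

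| (*a*, *b*) | Section 6.0 | Footnote, 'and' | Footnote, literal 'or' | Proposed footnote |
|---|---|---|---|---|
| (5, 3) | stop | delay allowed | delay allowed | delay not allowed |
| (8, 5) | stop | delay allowed | delay allowed | delay not allowed |
| (12, 1) | stop | delay not allowed | delay allowed | delay not allowed |
| (2, 6) | stop | delay not allowed | delay allowed | delay not allowed |
| (12, 6) | stop | delay not allowed | delay not allowed | delay not allowed |
| (5, 1.5) | no stop | delay allowed | delay allowed | delay allowed |
| (8, 2) | no stop | delay allowed | delay allowed | delay allowed |
| (3, 5) | no stop | delay allowed | delay allowed | delay allowed |

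The first two rows conflict on either reading. Rows three and four conflict only on the literal reading. The last three rows show that the proposed wording does not stop anyone whom Section 6.0 would keep eligible.

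**The case against.** **Precedence.** Section 6.0 uses mandatory language, while the footnote is permissive. The Criteria to Resume Treatment defer to the stop rules twice: once for the combined liver case, and once for long delays, "except as specified in discontinuation section". The algorithms are described as recommended or suggested. A careful reader would put Section 6.0 first, and a physician who follows it breaches nothing. Section 1.3 also asks for medical-monitor consultation on moderate and high-grade hepatic events, and Section 6.0 has a stop at the investigator's judgment. All of this stands and lowers the risk. None of it says which text governs, and the footnote sits in an algorithm that sites are recommended to follow.

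**The missing flowchart.** The footnote qualifies a box in a figure that is not shown, and that box might limit its scope. This stands as a limit on confidence: the conflict is established on the visible text only.

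**The literal 'or'.** The footnote's limits match the two single-parameter limits in Section 6.0, so 'and' was probably intended. This is fair, and it is why the point rests on the 'and' reading, where the conflict remains.

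**A stronger inference: re-treatment after a first grade 3 colitis or uveitis.** The subsections on other immune-mediated adverse events, in Sections 1.3 and 6.0, allow dosing to resume after a steroid taper and name recurrent severe and life-threatening reactions as permanent stops. A reader might infer that a first grade 3 colitis or uveitis may be re-treated, contrary to "Grade 3 drug-related uveitis, pneumonitis, bronchospasm, diarrhea, colitis, neurologic adverse event, hypersensitivity reaction, or infusion reaction of any duration requires discontinuation". The documents do not support calling that a contradiction:

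- Neither subsection says its two stop conditions are the only ones, so they can stand alongside the Discontinuation Criteria.
- Resumption is permissive and depends on severity. It fits grade 2 events, grade 3 skin events, and unlisted grade 3 events too short to meet "Any Grade 3 non-skin, drug-related adverse event lasting > 7 days".
- The Discontinuation Criteria themselves provide for tapers: "Dosing interruptions to allow for prolonged steroid tapers to manage drug-related adverse events are allowed".
- In Section 1.3 the subsection follows separate gastrointestinal and uveitis subsections. In Section 6.0 colitis and uveitis are named as examples in the monitoring paragraph, not in the resumption sentence.

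The Section 6.0 wording could be misread and is worth an optional clarification.

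**Conclusion.** The Appendix 4 footnote is wrong as written. On its visible text it permits delay for drug-related elevations with AST/ALT above 3 and up to 8 x ULN together with bilirubin above 2 and up to 5 x ULN, all of which Section 6.0 makes a permanent stop. Read literally, it also permits delay when only one single-parameter limit is exceeded.

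The size is a range of laboratory values, not a rate; the documents do not allow a count of affected patients. The conclusion assumes that the unseen flowchart box does not already exclude combined elevation. Severity is minor to should-fix: the consequence is for patient safety and consistent dosing, and the response-rate decision rule is unaffected.

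**What to change.** 1. Replace the condition in the Appendix 4 footnote with: *AST/ALT ≤ 8 x ULN and T.bili ≤ 5 x ULN, and not concurrent AST/ALT > 3 x ULN with T.bili > 2 x ULN*.
2. Add to the Discontinuation Criteria in Section 6.0: *A patient who meets these Discontinuation Criteria for toxicity stops permanently even if an appendix algorithm or other text allows delay or resumption; other toxicity stops in this protocol still apply.* The last clause makes clear that stops stated elsewhere remain, such as those for SJS/TEN and for recurrent severe immune reactions. It is confined to toxicity so that it does not reach the day-70 progression rule in the Study Calendar notes, which differs from the Treatment Beyond Progression text and Section 14.0 and should be settled separately.
3. Optionally, note in the Section 6.0 subsection on other immune-mediated adverse events that resumption after a taper applies only to events that do not meet the Discontinuation Criteria.

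The cost is amendment wording in one footnote and one added sentence, plus one clarified paragraph if item 3 is taken up, and a memo to sites. No new procedures, visits or data are needed.
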